10.1.5. Adjustment for multiplicity

The results from the analyses of the primary and secondary endpoint will be adjusted for multiple testing by a Bonferroni correction to keep a family-wise type 1 error of 5%. The Bonferroni correction for 2 endpoints correspond to evaluate the difference between products as significant if the p-value is less than 0.025. For the analysis of the exploratory endpoints no adjustment for multiple testing will be applied.

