10.1. Statistical design, method, and analytical procedures

The primary objective will be evaluated by analysing the primary endpoint whereas the secondary objective will be evaluated by analysing the secondary endpoint. The analyses of the exploratory endpoints will be used to further evaluate and explore the primary and secondary objectives.

All baseline measurements, endpoints and assessments will be summarized by descriptive statistics and/or listed. Endpoints and assessments will be summarized by product and time for evaluation, if relevant. Descriptive statistics for continuous variables are presented with N, Mean, SD (standard deviation), Median, Min and Max, where N denotes the number of subjects contributing with non-missing data. For discrete variables, descriptive statistics are presented with N and percentage, where percentage is based on the total number of subjects/observations with non-missing data.

All statistical analyses are made with SAS version 9.4 (SAS Institute Inc., Cary, NC)

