10.2. Sample size

The Emotional impact score (scale from 0-100) will be measured every 2nd week and all measurements will be part of the primary analysis whereas the primary comparison will be evaluated at the end of each test period.

The sample size calculation is based on a simplified model (paired 2-sided t-test). The result of the analysis will be adjusted for multiple testing and therefore a test level of 0.025 will be applied in the sample size calculation. Based on data from the previous CP308 investigation (PP population), it is assumed that the total standard deviation of the primary endpoint is 20.6 and that the total variation 20.6² is divided so that the residual variation is 14.4².

Based on the above assumptions 108 subjects should answer the questionnaires at the end of each test period to ensure a power of 81%, if the true difference between the two treatments (with and without HeyloTM) is 6 (minimal important difference is in the range of 5-10 according to the validation of the OLI score) [7]. To take a potential drop-out (25%) into account it is recommended to include 144 subjects.

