10.3. Level of significance and power

A two-sided significance level of 5% will be applied. For a description of the power see section 10.2 above.

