10.4. Pass/fail criteria

The purpose of the investigation is fulfilled if a statistically significant improved mean difference in the primary or secondary endpoint is obtained with the test product compared to Standard of Care.

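### Optional gain, not an error: Holm in place of Bonferroni keeps the family-wise 5% and makes a second significant endpoint easier to claim, with no extra subjects

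*Combined protocol and SAP*

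**What the plan says.** Section 10.1.5 defines a family of two endpoints, primary and secondary. Their results are to be "adjusted for multiple testing by a Bonferroni correction to keep a family-wise type 1 error of 5" percent, and the rule follows: "The Bonferroni correction for 2 endpoints correspond to evaluate the difference between products as significant if the p-value is less than 0.025". Exploratory endpoints are left unadjusted. Section 10.2 is consistent with this: because of the adjustment, "therefore a test level of 0.025 will be applied in the sample size calculation". Section 10.3 makes the tests two-sided.

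Two further passages bear on the choice. Section 10.1 gives each objective its own test: "The primary objective will be evaluated by analysing the primary endpoint whereas the secondary objective will be evaluated by analysing the secondary endpoint". Section 10.4 counts the investigation as successful on "a statistically significant improved mean difference in the primary or secondary endpoint". No stepwise procedure is mentioned anywhere.

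**The concern.** Nothing here is wrong in the sense of invalid. The point is efficiency. The plan has two objectives, each decided by its own endpoint, so whether the second endpoint is also significant is a result in its own right. Plain Bonferroni never passes on the alpha of a hypothesis already rejected. Once one endpoint has p < 0.025, the other must still reach 0.025, although the family-wise error would remain at or below 5% if it were tested at 0.05.

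Example: with p < 0.001 on one endpoint and p = 0.04 on the other, Bonferroni supports one objective and Holm supports both. What is at stake is the claim on the second objective, not the overall pass/fail result.

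**Working it through.** **Inputs from section 10.2.** Difference 6; residual SD 14.4 ("the total variation 20.6² is divided so that the residual variation is 14.4²"); 108 subjects with both assessments; two-sided level 0.025; stated power 81%; drop-out 25%.

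**Inputs the documents do not give.** There is no effect, SD or power for the WHODAS participation score, and no correlation between the two test statistics. I assume a secondary with no effect, with 40% or 50% power at 0.025, or with the same power as the primary, and a correlation of 0 or 0.7.

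**The plan's own figures.**
- Threshold: 0.05/2 = 0.025.
- Enrolment: 108/(1 − 0.25) = 144.
- SD of the paired difference: 14.4 × √2 = 20.36. Standard error: 20.36/√108 = 1.960. Standardised shift: 6/1.960 = 3.062.
- Two-sided normal critical values: 2.2414 (level 0.025) and 1.9600 (level 0.05).
- Power at 0.025: 79.4% by normal approximation and 78.4% by the noncentral t, against the stated 81%. That gap is a separate matter and does not affect the comparison below, which uses the normal approximation throughout.

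**Error control under Holm.** The smaller p-value is tested at 0.025 and, only if it is significant, the other at 0.05.
- Both nulls true: a false claim needs the smaller p-value below 0.025, which is exactly the Bonferroni event. The error is the same for both procedures: 4.94% at correlation 0, 4.65% at 0.5, 4.30% at 0.7.
- One null true: it can be rejected only if its own p-value is below 0.05, so the error cannot exceed 5%. With the planned primary effect and no secondary effect, false secondary claims are 2.5% under Bonferroni and 4.5% (correlation 0) or 4.0% (0.7) under Holm.

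**Power.** For each endpoint, Holm adds to the Bonferroni power the probability that this endpoint has p between 0.025 and 0.05 while the other has p < 0.025. For the primary:

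P(Holm) = P(|Z₁| > 2.2414) + P(1.9600 < |Z₁| ≤ 2.2414 and |Z₂| > 2.2414)

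Bivariate normal probabilities in %, Bonferroni → Holm:

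| Secondary power at 0.025 (shift) | Corr. | Primary | Secondary | Both | At least one (same for both) |
|---|---|---|---|---|---|
| no effect (0) | 0 | 79.4 → 79.6 | – | – | – |
| no effect (0) | 0.7 | 79.4 → 79.5 | – | – | – |
| 40% (1.988) | 0 | 79.4 → 82.2 | 40 → 48.8 | 31.8 → 43.4 | 87.6 |
| 40% (1.988) | 0.7 | 79.4 → 80.1 | 40 → 49.9 | 38.8 → 49.5 | 80.6 |
| 50% (2.241) | 0 | 79.4 → 82.9 | 50 → 58.8 | 39.7 → 52.0 | 89.7 |
| 50% (2.241) | 0.7 | 79.4 → 80.6 | 50 → 59.4 | 47.8 → 58.4 | 81.6 |
| equal (3.062) | 0 | 79.4 → 85.0 | 79.4 → 85.0 | 63.0 → 74.3 | 95.8 |
| equal (3.062) | 0.7 | 79.4 → 83.5 | 79.4 → 83.5 | 70.5 → 78.8 | 88.3 |

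**On the outcome scale.** If the secondary is significant at 0.025, the mean primary difference needed for significance at n = 108 falls from 2.2414 × 1.960 = 4.39 to 1.9600 × 1.960 = 3.84 points (4.45 to 3.88 with t critical values).

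**Sample size.** The first step is still at 0.025, so the calculation in 10.2 is untouched.

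**The case against.** The strongest reply is that the plan has no defect here. Family, level and threshold are stated, the sample size agrees with them, and the criterion in section 10.4 is met with exactly the same probability under either procedure. Nothing in the plan requires both endpoints to be significant. All of that stands, which is why this is an optional improvement only. It does not remove the benefit, since section 10.1 assigns each objective its own endpoint.

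The size of the gain depends on assumed inputs. This also stands. The direction is certain, but the gain in primary power runs from 0.1 to 5.6 points, and the top of that range needs a secondary as well powered as the primary, which the documents do not support. The OLI items concern leakage over the last 7 days; WHODAS asks about health conditions in general over 30 days, so a less sensitive secondary is plausible.

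There are real costs. False secondary claims become more frequent when only the primary effect is true, though still below 5%. Bonferroni has matching 97.5% intervals and Holm has no equally simple counterpart, so an endpoint can be Holm-significant while its 97.5% interval includes zero. Section 10 sets no interval level, so the mismatch arises only if such intervals are reported. Finally, in an open-label trial a late switch to a more permissive rule would draw criticism, so timing matters.

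**Conclusion.** The point holds as an optional gain. Bonferroni at 0.025 is valid and consistent with section 10.2. Holm is uniformly at least as powerful, needs no further assumption, and keeps the family-wise 5%.

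Where the secondary effect is real, the chance of supporting both objectives rises by 8.3 points (equal power, correlation 0.7) to 12.3 points (50% secondary, correlation 0). A secondary with 40% to 50% power gains about 9 to 10 points; one with equal power gains 4 to 6. The gain in primary power is small unless the secondary is well powered. These sizes rest on the assumed secondary power and correlation and on the normal approximation; error control and the unchanged chance of at least one success do not.

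**What to change.** In section 10.1.5, replace the Bonferroni rule with Holm: compare the smaller of the two p-values with 0.025 and, only if it is significant, compare the other with 0.05. Keep 0.025 in section 10.2, so 108 evaluable and 144 enrolled subjects are unchanged. Holm also preserves the either-endpoint rule in 10.4, because the secondary can still succeed when the primary fails; a fixed sequence starting with the primary would not allow that.

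State that significance follows the Holm decision and that a 97.5% interval may include zero for an endpoint with p between 0.025 and 0.05. The chance of this is 0.1–5.6% for the primary over the scenarios above, and 8.8–10.0% for a secondary with 40% power.

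The cost is wording plus the amendment steps in section 12: signed agreement of sponsor and principal investigator, a Change Log entry, and ethics committee notification if the change is judged significant. It must be fixed before the statistician is unblinded at database lock (section 5.8). If the sponsor values matching intervals more than the extra power, keeping Bonferroni is a sound choice.

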10.2. Sample size

The Emotional impact score (scale from 0-100) will be measured every 2nd week and all measurements will be part of the primary analysis whereas the primary comparison will be evaluated at the end of each test period.

The sample size calculation is based on a simplified model (paired 2-sided t-test). The result of the analysis will be adjusted for multiple testing and therefore a test level of 0.025 will be applied in the sample size calculation. Based on data from the previous CP308 investigation (PP population), it is assumed that the total standard deviation of the primary endpoint is 20.6 and that the total variation 20.6² is divided so that the residual variation is 14.4².

Based on the above assumptions 108 subjects should answer the questionnaires at the end of each test period to ensure a power of 81%, if the true difference between the two treatments (with and without HeyloTM) is 6 (minimal important difference is in the range of 5-10 according to the validation of the OLI score) [7]. To take a potential drop-out (25%) into account it is recommended to include 144 subjects.

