10.1.2 Statistical analysis of the primary endpoint

The Emotional impact score (scale from 0-100) measured every 2^{nd} week will be analysed by a linear mixed model. The model includes a fixed effect of product (standard of care, HeyloTM), a fixed effect of time (2, 4, 6 and 8 weeks), a fixed interaction between product and time, a fixed period effect and a random effect of subject.

The difference between standard of care and $Heylo^{TM}$ at week 8 will be estimated and tested (the primary comparison). Other combinations of differences can be estimated, if relevant.

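### The 81% power in section 10.2 does not follow from the inputs printed beside it, which give 78.4% for 108 completing pairs

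*Combined protocol and SAP*

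**What the plan says.** Section 10.2 (Sample size) sets out the calculation: "The sample size calculation is based on a simplified model (paired 2-sided t-test"). Because two endpoints share the type I error, "a test level of 0.025 will be applied in the sample size calculation". This agrees with section 10.1.5, where the rule is to "evaluate the difference between products as significant if the p-value is less than 0.025".

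From an earlier investigation (CP308, per-protocol population), section 10.2 takes a total standard deviation (SD) of 20.6 for the primary endpoint and a residual variance of 14.4². The true difference is set at 6 points. On these assumptions "108 subjects should answer the questionnaires at the end of each test period to ensure a power of 81" per cent, and an allowance of 25% for drop-out raises 108 to 144 subjects.

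The planned analysis is wider than the planning test. Section 10.2 notes that "all measurements will be part of the primary analysis", and section 10.1.2 specifies a linear mixed model with, among other terms, "a fixed interaction between product and time, a fixed period effect and a random effect of subject". Section 10.3 adds no power figure: "For a description of the power see section 10.2 above".

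**The concern.** A power figure should follow from the test, level, variance, difference and sample size given with it. Section 10.2 prints all five, and they yield a lower figure than the one stated. Since section 10.3 only points back to 10.2, the 81% is the plan's sole power statement. If it is wrong, the type II error of the planning test is 21.6% rather than 19%, and the design falls just below 80% power when the text places it just above. Anyone who checks the sample size will be unable to reproduce it.

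**Working it through.** **Inputs, all from section 10.2:** two-sided paired t-test; level α = 0.025; total SD 20.6; residual SD 14.4; true difference 6; n = 108 pairs; drop-out 25%.

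**The drop-out step reproduces.** 108 / (1 − 0.25) = 144.

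**The power does not.**

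1. SD of a within-subject difference: √2 × 14.4 = 20.365.
2. Standard error: 20.365 / √108 = 1.960.
3. Noncentrality: 6 / 1.960 = 3.062.
4. Critical value: t(0.9875; 107 df) = 2.273.
5. Power from the noncentral t distribution: 0.7836, or **78.4%**. A simulation of 200,000 trials gave 78.5%.

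**Variants that might have produced 81%.** The correlation implied by the two SDs is 1 − 14.4²/20.6² = 0.511.

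| Variant, 108 pairs | Power |
|---|---|
| Paired t-test as described | 78.4% |
| Normal approximation | 79.4% |
| 106 df | 78.3% |
| 214 df (2n − 2) | 78.9% |
| Total SD 20.6, correlation rounded to 0.51 | 78.2% |
| Total SD 20.6, correlation rounded to 0.50 | 77.3% |
| Residual SD 14.35 to 14.45 (rounding of 14.4) | 78.7% to 78.1% |
| Level 0.05 two-sided, or 0.025 one-sided | 85.9% |
| 14.4 taken directly as SD of the difference | 97.9% |
| Total SD with no correlation (SD of difference 29.1) | 45.0% |

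None returns 81%.

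**What 81% would need, changing one input at a time:**

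- *Pairs.* 108 gives 78.4%, 113 gives 80.4%, 114 gives 80.8% and 115 gives 81.1%. So 115 is the first number to reach 81%, and 114 the first to round to it. Of 144 randomised, 115 completers is 115/144 = 79.9% retention, or 20.1% drop-out.
- *Residual SD.* 14.0 gives 80.8%. A power that rounds to 81% (80.5% to 81.5%) needs an SD between 14.05 and 13.89.
- *Difference.* About 6.19 (6.15 to 6.22 for a power that rounds to 81%).
- *Level.* About 0.031 (0.030 to 0.033).

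**The case against.** The arithmetic is hard to contest; the case on the other side is about weight and about which figure to change.

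**The gap is small and concerns a planning proxy.** It is 2.6 points, or 1.6 against the normal approximation. The actual analysis uses all two-weekly measurements, so its power may differ, and section 10.1.1 itself describes the trial as exploratory. This stands as a limit on the consequence: 78.4% is not the power of the primary analysis, which cannot be computed from the plan. It does not rescue the figure, because section 10.2 attributes 81% to the simplified test.

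**The trial may reach 81% anyway.** With drop-out of about 20% or less, 144 randomised subjects leave at least 115 completers. That is true, but the plan assumes 25% and attaches the 81% to 108.

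**Another printed figure may be the slip.** For example, 115 pairs with 20% drop-out gives 115/0.80 = 143.75, which rounds up to 144 and would reproduce both 81% and 144. A slightly different difference or level would also do it. The plan supports none of these: it prints 108, 25%, 6 and 0.025, the first two give 144 exactly, and the level is confirmed in section 10.1.5. The point that stands is that the plan does not show which figure is wrong, so the original calculation has to be looked at before the text is changed.

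**Conclusion.** The concern holds. On the printed inputs, the paired t-test with 108 pairs has 78.4% power, not 81%. The shortfall is 2.6 points, equivalent to 7 completing pairs (115 against 108). Rounding and the usual variants do not explain it.

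The result assumes that the residual variance of 14.4² is the within-subject variance of a single measurement, so that a difference between periods has variance 2 × 14.4². That is the standard reading of a total variance split into parts; the CP308 data behind it are not in the plan. The statement that 108 pairs need a residual SD of about 14.0 holds with the difference at 6 and the level at 0.025.

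This is a real error in the plan's only power statement, worth correcting but modest in effect. It does not touch the endpoint, the analysis model, the multiplicity rule or the pass/fail criterion.

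**What to change.** Re-run the calculation and check each input against the one actually used. Unless that turns up a misprinted input, keep 108 completers and 144 randomised, and restate the power in section 10.2 as about 78%, for the simplified paired t-test at the two-sided 0.025 level and a true difference of 6. If a residual SD of about 14.0 was in fact used, correct the printed 14.4 and keep 81%. It would also help to say in section 10.2 that the figure applies to the simplified test and not to the mixed model.

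The cost is wording only: no extra subjects and no change to the analysis. The one drawback is a slightly less favourable power figure. Holding to 81% by raising the number of pairs instead would mean 115/0.75 = 153.3, so 154 randomised at the assumed drop-out; a gap of this size does not call for that.

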10.3. Level of significance and power

A two-sided significance level of 5% will be applied. For a description of the power see section 10.2 above.

10.4. Pass/fail criteria

The purpose of the investigation is fulfilled if a statistically significant improved mean difference in the primary or secondary endpoint is obtained with the test product compared to Standard of Care.

10.5. Interim analysis

There is no planned interim analysis in this investigation.

10.6. Statistical reason for termination of investigation

There will be no interim analysis and therefore no reason to terminate the investigation based on statistical considerations.

10.7. Deviation(s) from statistical design, method, or analytical procedures

Any deviations from the statistical plan will be documented in the clinical investigation report.

11. Data management

11.1. Data collection and data management

11.1.1. Data Collection in the clinical investigation

Data management and the final statistical analyses of all measurements described in this protocol are carried out by the Medical Affairs, Coloplast A/S.

Data will be collected through an electronic data capturing (EDC) system on electronic Case Report Form (eCRF), internet-based case report form. This system will be used to record all subject information collected in the investigation for secure data tracking and centralised data monitoring ("remote monitoring") done by monitors, as defined in the monitoring plan.

The EDC system used is ______. The system is designed to be compliant with the FDA requirements of 21 CFR part 11. It is a validated data management system allowing only qualified and trained personnel to enter the system. The system has full audit trail and electronic signature.

The Principal Investigator or delegate will enter data in a part of the system referred to as the eCRF. The subjects will receive a link to the system to enter their registrations in a part of the system referred to as the subject questionnaire.

The sponsor will be responsible for training the investigator or delegate, in completion of the eCRF.

Principal Investigator, or delegate will perform primary data collection directly into the eCRF or drawn from source-document (medical records) reviews. The eCRF will be completed on a continuous basis starting from the point of enrolling the subject to final follow up.

The eCRF will be completed by the investigator, or delegate, who have signed the Site Personnel Signature and Delegation List and Clinical Investigation Training Log. It will be the responsibility of the Principal Investigator to ensure that all measurements and observations are correctly noted in the eCRF.

All assessments and observations throughout the investigation for each subject must be carefully recorded in an eCRF during the visit or immediately after. The eCRF makes it possible to enter data right away when they are obtained. This is the preferred way of collecting data. In case this is not possible the data should be entered no later than 7 days after the visit / procedure.

Adverse events should be registered following the timelines described in the Adverse Event section.

In the unforeseen situation, where clinical investigation personnel cannot establish connection to the EDC system a paper CRF (pCRF) has been printed and supplied by sponsor.

The investigator will keep a separate list of the subjects' ID numbers, names, and addresses in a locked room/cabinet. Only data referred to in this clinical investigation plan will be recorded in the CRFs.

11.1.2. Database Management, Queries and Quality Control

The data management system has restricted role-based access control. The principal investigator or delegate must be trained in the system prior to getting access. The training must be completed before access to the investigation is granted. Only the principal investigator, or delegate, will be authorised to enter data in the eCRF.

The monitor, using his/her personal login information shall verify all critical data points against the source documents and issue electronic queries for the authorised clinical investigation personnel to respond, as defined in the monitoring plan.

The principal investigator, using his/her personal login information shall sign each eCRF.

Automated, real time access to the data enable control on study compliance and safety assessments.

A critical quality control will be performed by the sponsor's data management team and queries issued where needed. Such queries will be reviewed by the monitor and must be resolved by the clinical investigation personnel.

At the end of the study a formal data review meeting will be performed before the database will be locked.

A full audit trail ensures, that each user's (clinical investigation personnel, monitor, sponsor, data manager) access to and actions in the system is tracked.

The Data Management Procedures are further described in the Data Management SOPs.

